Cranial Electrotherapy Stimulation on Acute Stress

NCT06034496

May 8, 2025

Statistical Analysis Plan (SAP)

Manipulation Check. To ensure effective stress induction, we will assess AA, HR, CORT, and subjective stress responses to stress exposure during the baseline session. We will compare sampled AA levels from immediately prior to (pre) to immediately after stress exposure (i.e., time points pre and 0-min post-task). We will compare mean HR from immediately prior to (pre) to during stress exposure (i.e., during the RMT, SOT, DMT). We will compare sampled CORT levels from immediately prior to (pre) to 0-minutes after stress exposure (i.e., time points pre and 0-min post-task). We will compare STAI-S scores from immediately prior to (pre) to immediately after stress exposure. For these analyses, we will conduct paired t-tests.

Physiological & Biochemical Responses to CES. To evaluate physiological and biochemical responses to CES, we will use analysis of variance (ANOVA)s to assess the effect of CES Group (2: Active, Sham), Session (2: Baseline, Follow-up), and Time (pre-task, 0-min, 20-min, 40-min, 60-min post-task) on each of six outcome measures: HR, HRV, RR, tonic PD, AA, and CORT (number of levels varies as a function of outcome measure and is described as follows). Each response measure will be assessed in a discretized time series based on its sampling times; continuous measures (e.g., HR) will be discretized into pre-stress versus during-stress time periods. For HR, HRV, respiration, and tonic PD, pre-stress will be calculated as the mean of the one-minute time period immediately preceding the beginning of the tasks, and during-stress will be calculated as the mean of the entire behavioral task performance. For AA and CORT, we will include all five time points in the analysis (i.e., pre-task, 0-min, 20-min, 40-min, 60-min post-task).

Cognitive & Affective Responses to CES. To evaluate the cognitive and affective responses to CES, we will use mixed ANOVAs to assess the effect of CES Group (2: Active, Sham) and Session (2: Baseline, Follow-up) on each of four cognitive outcome measures, and one affective outcome measure. Cognitive measures include RMT overall accuracy, SOT absolute angular direction error, SOT absolute distance estimate error, DMT discriminability (d'), and DMT response criterion (c). Affective measures include STAI-S scores, and we will use a mixed ANOVA to assess the effect of CES Group (2: Active, Sham), Session (2: Baseline, Follow-up), and Time (pre-task, 0-min, 20-min, 40-min, 60-min post-task).

Mixed ANOVAs will be conducted using package *rstatix* (ver. 0.7.0; Kassambara, 2023) in R (ver. 4.1.2). Mixed ANOVA assumptions will be checked using package *rstatix* (ver. 0.7.0; Kassambara, 2023) in R (ver. 4.1.2). Extreme outliers will be identified, removed, and mean imputed. Normality will be assessed with Shapiro-Wilk Normality Test; non-normal data will be log-transformed. Homogeneity of variance will be assessed with Levene's Test and confirmed all groups had the same or similar variance. Mauchly's test of sphericity will be automatically conducted and corrected for in the mixed ANOVAs analysis.

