Soldiers are continually exposed to acute stressors during training and operations, activating a cascade of biochemical changes in the body, including an initial sympathetic-adrenal medulla (SAM) catecholamine-related response, and a slower-moving hypothalamic-pituitary-adrenal (HPA) glucocorticoid-related response (Angelova et al., 2021; Axelrod & Reisine, 1984; Buchheim et al., 2019; Charmandari et al., 2005; Gagnon & Wagner, 2016; McEwen, 2007; Padgett & Glaser, 2003). The diverse effects of acute stress on neurotransmitters and the central nervous system are associated with similarly diverse perceptual and cognitive effects, generally related to the intensity of experienced stress and the processes demanded by specific mental tasks. For example, mild-to-moderate acute stress can improve performance on relatively basic (or well-learned and rehearsed) perceptual and cognitive tasks, such as simple reaction time and verbal memory retrieval, perhaps owing to activation of the ascending reticular activating system (ARAS) (Arnsten, 2009; Broadbent, 1971; Brunyé et al., 2021a, 2021b; De Cicco et al., 2018; Hupbach & Fieman, 2012; Shields et al., 2019). Moderate-to-high acute stress, in contrast, can negatively influence performance on tasks more demanding of executive processes and spatial memory retrieval, perhaps owing to HPA-related activation and brain regions (e.g., prefrontal cortex, hippocampus) with high glucocorticoid receptor densities (Arnsten, 1998, 2009; Brunyé et al., 2016, 2019; Cerqueira et al., 2007; Luine et al., 1994; Olver et al., 2015; Richardson & VanderKaay Tomasulo, 2011; Shields et al., 2015, 2016).

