1. Two extant research studies suggest that 300 μ A (Bystritsky et al., 2008; Overcash et al., 1989) and up to 1500 μ A (Smith et al., 1994) are effective at lowering anxiety, in line with the conclusions of a review examining CES effects on anxiety and stress (De Felice, 1997).
2. Most of the data from our prior research with the device shows the predicted pattern of results, for example lower heart rate variability and respiration rate with CES (vs sham); however, the pattern is numerical only and does not reach traditional significance levels. We believe that higher intensity CES may

amplify these previously noted patterns; of course, this is an empirical question and cannot be answered without additional data collection.

3. This procedure of individualized thresholding is congruent with manufacturer's recommendations, and they report seeing the most reliable anxiolytic-like effects with this procedure. Also, the procedure of individualized thresholding and minimum intensity ($\geq 250\mu\text{A}$) is congruent with the Special Operations Command's (SOCOM) current use of the device during military training and operations, where they report anecdotal success for stress mitigation.

Second, rather than a single 20-minute session of CES administration, we will use daily administration (20-minutes/day) over the course of 4-6 weeks.

These first two modifications are being made to better conform with the device manufacturer's (Electromedical Products International, Inc., Mineral Wells, TX) recommendations for CES administration.

Finally, to elicit a more robust stress response that activates both SAM and HPA activity, we will increase the intensity (to level 3 of 5) of our torso shock administration. With these changes, we make four primary hypotheses:

H1: Biochemistry: We hypothesize that Active vs Sham CES will reduce biochemical responses to stress, including salivary alpha amylase as an indicator of SAM activity and salivary cortisol as an indicator of HPA activity.

H2: Physiology: We hypothesize that Active vs Sham CES will reduce physiological responses to stress, including heart rate, heart rate variability, respiration rate, and pupil diameter.

H3: Emotion: We hypothesize that Active vs Sham CES will reduce subjective experiences of stress, including responses on the STAI.

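### The cortisol manipulation check tests only the sample at task end, so it can miss HPA activation if the cortisol rise peaks later

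*SAP*

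**What the plan says.** The SAP opens with a manipulation check on the baseline session: "To ensure effective stress induction, we will assess AA, HR, CORT, and subjective stress responses to stress exposure during the baseline session". For alpha amylase: "We will compare sampled AA levels from immediately prior to (pre) to immediately after stress exposure". For cortisol: "We will compare sampled CORT levels from immediately prior to (pre) to 0-minutes after stress exposure". The method is the same throughout: "For these analyses, we will conduct paired t-tests". The SAP gives no reason for using the same window for both salivary markers.

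The protocol separates the two stress systems. Section 2.0 (Acute Stress) describes an initial SAM response followed by "a slower-moving hypothalamic-pituitary-adrenal (HPA) glucocorticoid-related response". Hypothesis H1 assigns the markers: "salivary alpha amylase as an indicator of SAM activity and salivary cortisol as an indicator of HPA activity". Section 2.0 (The Present Study) explains that shock intensity was raised "to elicit a more robust stress response that activates both SAM and HPA activity", after the previous study had modulated SAM measures but not HPA measures.

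Section 6.0 (Saliva Sampling and the example baseline schedule) places stress testing at 0920-0945. Post-task saliva samples follow at 0945-0950, 1005-1010, 1025-1030 and 1045-1050, which the SAP labels 0, 20, 40 and 60 minutes post-task. The SAP enters all five cortisol time points into the Group x Session x Time ANOVA. Only the 0-min sample is compared with pre in the manipulation check.

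**The concern.** The check applies the fast marker's time point to the slow marker. Whether the stronger stressor activates HPA is something this study was redesigned to achieve, and the cortisol contrast is the designated test of it. If the cortisol rise peaks after task end, a single comparison at task end sees only part of it and may be non-significant although the stressor worked.

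The sponsor could then conclude, as in the previous study, that HPA did not respond. A null CES effect on cortisol, which is half of H1, could be put down to a failed stressor when it should count as evidence about CES. The samples that could settle the matter are already planned.

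**Working it through.** **The plan's own figure.** Protocol section 5.2 gives f = 0.47, power 0.80, alpha 0.05 and total N = 38. For two groups d = 2f = 2 x 0.47 = 0.94. A two-sided two-sample t-test needs 19 per group, total 38, with exact power 0.805. The figure reproduces. It concerns subjective anxiety between groups, so the plan contains no power statement for cortisol.

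**Timing, from the example schedule.**
- Stress onset to 0-min sample: 0920 to 0945-0950 = 25-30 minutes.
- Stress onset to 20-min sample: 0920 to 1005-1010 = 45-50 minutes.
- Only scheduled pre-stress saliva sample: 0820-0825, which is 55-60 minutes before 0920.

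**Power of the planned check.** Input: n = 40 complete data sets (section 5.2). Both groups contribute, because the check uses the baseline session. Paired t-test, df = 39, noncentrality = dz x sqrt(40), two-sided alpha 0.05, critical t = 2.023. The documents give no cortisol effect size or time course, so both the peak dz and the share of the rise present at 0-min are assumptions.

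| Assumed peak dz | All of rise at 0-min (or test at peak) | 75% at 0-min | 50% at 0-min | 25% at 0-min |
|---|---|---|---|---|
| 0.4 | 0.69 | 0.46 | 0.23 | 0.09 |
| 0.5 | 0.87 | 0.64 | 0.34 | 0.12 |
| 0.8 | 0.999 | 0.96 | 0.69 | 0.23 |

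Example: for dz = 0.5 with 75% present, the effect is 0.375 and the noncentrality is 0.375 x 6.325 = 2.37, giving power 0.64. The chance of missing a real response goes from 1 - 0.87 = 13% at the peak to 36%, 66% or 88% at 75%, 50% or 25%.

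The planned test reaches 80% power only if dz at the 0-min sample is about 0.455 or more. If half the rise is present then, the peak must be about 2 x 0.455 = 0.91.

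**The mirror case.** If the peak is at 0-min, the planned test has the full 0.87 for dz = 0.5. A test moved to 20 minutes would have 0.64 or 0.34 if 75% or 50% of the rise remained. Replacing one sample by the other therefore only exchanges one risk for its opposite.

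**Testing both.** With two contrasts under Bonferroni (alpha 0.025 each, critical t = 2.331), power of the contrast at the peak sample for dz = 0.5 is 0.79. Testing all four post-task samples (alpha 0.0125 each) gives 0.71.

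**The case against.** The strongest defence is that 0-min is counted from the end of the task. The sample comes 25-30 minutes after stress begins, and shocks follow errors during the task, so the response to its early part may already be present. The documents call HPA slower but give no latency in minutes. This stands: a reader might infer that a task-end sample cannot yet contain the cortisol response, and the documents do not support that. They support only that it may not contain all of it.

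Second, a reader might infer that the later cortisol samples go unused. They do not: all five time points enter the ANOVA, where a delayed rise could appear as a Time effect. This is a partial answer. That effect pools both groups and both sessions, including follow-up after 20 CES sessions, and it is not the designated baseline check.

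Third, a reader might infer that a failed check would invalidate or block the cortisol test in H1. Nothing in the SAP makes the CES analysis conditional on the check, and no action follows from a null result. Alpha amylase, heart rate and STAI-S also contribute to the check. A false negative would leave the Group estimate and its test unchanged; only the interpretation would suffer.

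**Conclusion.** The point holds in limited form. The plan tests its slower marker only at the faster marker's time point, without justification, although later samples are scheduled and HPA activation is a stated aim. If the cortisol peak falls after task end, the check can miss a real response: for an assumed peak dz of 0.5 and n = 40, power falls from 0.87 to 0.64 or 0.34 when 75% or 50% of the rise is present at 0-min. If the whole rise is present at 0-min, the loss is zero. The documents do not say which case applies, so the size of the risk cannot be fixed. What is at stake is the conclusion on HPA activation and the reading of a null cortisol result, and the validity of the CES comparison is unaffected.

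A related inconsistency also needs settling. The SAP describes the pre sample as taken immediately before stress, whereas the example schedule places the only pre-stress saliva sample about an hour earlier. The Saliva Sampling text in section 6.0 lists six sampling moments, one of them directly before testing, but counts five.

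**What to change.** In the SAP's Manipulation Check, pre-specify two paired contrasts for cortisol at baseline, pre v 0-min and pre v 20-min, with Bonferroni or Holm correction. Declare HPA activation if either shows a significant rise. Keep pre v 0-min for alpha amylase. State in the SAP which saliva sample is the pre value, and bring the SAP wording, the Saliva Sampling text and the example schedule into agreement.

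The statistical price under Bonferroni is a fall in power at the peak sample from 0.87 to about 0.79 for dz = 0.5, in exchange for protection if the peak comes after task end. A peak at 40 or 60 minutes would be only partly covered; covering every sample would lower the figure to 0.71. No additional samples or participants are needed, and the edit is a few SAP sentences. It should be made before the cortisol data are examined. The documents do not report whether that has happened; if it has, the added contrast should be labelled post hoc.

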H4: Behavior: We hypothesize that Active vs Sham CES will lead to increased performance on tasks typically degraded by stress exposure, including a recognition memory test and a spatial memory test.

3.0 Participant Population:

We expect to recruit up to 500 individuals, including Soldiers and civilians, to achieve a final sample size of 40 complete data sets. Our high recruitment number allows for Soldier group briefings (active-duty units at their home station and HRV cohorts at DEVCOM SC) which are routinely 30+ and can be upwards of 100 Soldiers.

We anticipate an approximately 40-50% attrition rate given our requirement to meet a minimum CES threshold of $300\mu\text{A}$ (i.e., a $250\mu\text{A}$ minimum CES intensity) and the prolonged study duration. To accommodate the potentially high attrition rate, we expect to recruit and consent up to 500 Soldiers and/or civilians, and schedule and enroll up to 100 Soldiers and/or civilians.

We are recruiting civilians in addition to military personnel because we have limited access to military personnel to conduct this research, and we have no a priori reason to believe that civilians will show markedly different stress responses, task performance, or CES responses relative to military personnel. In fact, most extant research examining the utility of CES for stress reduction is conducted with civilians. Because one of our tasks (marksmanship) could be considered geared towards military personnel, see

Section 15 for a description of possibly increased risk of psychological harm to civilians versus military personnel.

We will recruit participants 18-40 years of age, or 17 years if emancipated minor. This age range was chosen to represent the majority of Active Duty enlisted military personnel, which is under 41 years of age (*Defense, 2014*). There is no gender-based enrollment restriction.

Inclusion Criteria: Eligible individuals include those who:

1. Can sit and stand freely.
2. Have not used or experienced CES administration in the past.
3. Agree to have their data stored in a repository (database) for future use. Peer-reviewed scientific journal may require data to be stored in a repository as a condition for publication. Such repositories are online databases, in which coded data is linked (no link to participants personally) to the journal article citation.

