During the cognitive testing, if an incorrect response is provided by participants (e.g., > 45° absolute angular error during the spatial orienting task, incorrectly firing upon a friendly or incorrectly letting an enemy pass during the decision-making test), the system will automatically trigger a torso shock. The shock belt will be set at level 3, which (in our previous studies) participants tend to find uncomfortable and stressful, but not painful. If participants cannot tolerate the shock and ask for it to be disabled, we will pause data collection and give them a 5-minute rest period and ask whether they would like to try it again. If they respond *yes*, we will resume data collection (and repeat this rest-retry procedure as necessary). If they respond *no*, we will ask whether they are willing to be rescheduled and try again on another day; if they respond *no*, we will not reschedule. If they respond *yes*, we will reschedule the participant for another session. If during two consecutive sessions they cannot tolerate the shock, they will be dismissed from the study.

Upon completion of testing, participants will return to the private seating area, where they will complete the additional saliva sampling and STAI-S.

3. Saliva Sampling: Participants will provide saliva samples using the Salivabio Oral Swab (SOS) method from Salimetrics. This sampling method involves participants placing a hygienic absorbent swab under their tongue for 2 minutes, and then placing the swab into a vial. The advantage of the SOS method is that participants can do it entirely independently (opening the swab package, placing the swab under the tongue, removing swab from mouth, placing swab in the vial, closing the vial) and without direct contact from the experimenter. Using this method, saliva samples will be taken immediately prior to Questionnaires, immediately prior to Cognitive Testing Under Stress, immediately following Cognitive Testing Under Stress (accompanied by emotional state questionnaires), and at 20-minutes, 40-minutes, and 60-minutes after. In this manner, we will collect a total of 5 saliva samples during this Baseline session.

After completing this series of saliva samples, questionnaires, and tasks, participants will be briefed on the CES session procedures. Participants will then be released for the day. Overall, we expect the Baseline session to last approximately 3 hours, as detailed in the below example schedule:

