The final testing day will serve as the follow-up session to assess whether 20 sessions of Active (versus Sham) CES will impart any changes to the biochemical, physiological, affective, or behavioral responses to stress induction. This session will be held at approximately the same time of day as the thresholding and baselining session, within 5 days of the last daily CES session. The procedures for this session will precisely match the thresholding and baselining session but without the thresholding phase. After completing the final testing day, participants will have completed the study.

Data Analysis

We will analyze data from our biochemical, physiological, affective, and behavioral measures using Generalized Estimating Equations (GEEs) and/or Analyses of Variance (ANOVAs) to examine changes over the 20 CES sessions, changes from baseline to follow-up, and changes due to Active versus Sham CES. An effect will be deemed statistically significant if the likelihood of its occurrence by chance is $p < 0.05$; to reduce the likelihood of a Type I error, any follow-up comparisons (e.g., t-tests) will use a Bonferroni-corrected alpha criterion.

6.1 Additional Safeguards for Special Populations:

This research is funded by the Department of Defense, and the funding agency is interested in how military personnel respond to CES administration; for that reason, we will prioritize the recruitment of military personnel, and secondarily recruit from civilian populations as required to fulfill our sample size goal.

When recruiting military personnel to participate in this research, we will conform to additional safeguards for the protection of human subjects outlined in DoD Instruction (DoDI) 3216.02. These include additional safeguards to protect participants who may be more vulnerable to coercion or undue influence.

7.0 Investigational Medical Devices:

For the CES sessions, we will be using the Alpha-Stim AID cranial electrotherapy stimulator (CES) medical device, which is an FDA cleared, handheld medical device used for the treatment of anxiety, insomnia, and depression (i.e., AID; see Appendix D).

Because our study is using the device with healthy participants, the device is being used off-label in a manner that is for *investigational use only*. As detailed in the Informed Consent Form, this means that the device is being used in a study examining its safety or effectiveness, and not for the treatment, diagnosis, or prevention of any disorder.

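### The mixed ANOVAs for amylase, cortisol and STAI-S use only participants with all 10 values; prespecify a mixed model that uses every available value

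*SAP*

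**What the plan says.** The SAP (Physiological & Biochemical Responses to CES) crosses "CES Group (2: Active, Sham), Session (2: Baseline, Follow-up), and Time (pre-task, 0-min, 20-min, 40-min, 60-min post-task") and adds for the saliva outcomes: "For AA and CORT, we will include all five time points in the analysis". Under Cognitive & Affective Responses to CES, STAI-S has the same three factors. Heart rate, heart rate variability, respiration and pupil diameter are reduced to one pre-stress and one during-stress mean per session. The cognitive outcomes have one value per session.

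On software, the SAP says "Mixed ANOVAs will be conducted using package" rstatix in R, with Mauchly's test and a sphericity correction. Its one imputation rule replaces removed extreme outliers by a mean. It says nothing about a value that was never obtained.

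The Protocol (6.0, Data Analysis) left the method open, "using Generalized Estimating Equations (GEEs) and/or Analyses of Variance (ANOVAs"). The SAP kept only ANOVA. The Protocol (3.0) plans "to achieve a final sample size of 40 complete data sets" without saying what makes a data set complete. Its section 16.0 states that a withdrawn participant's data are destroyed and not analysed.

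**The concern.** A classical repeated-measures ANOVA works on one full row per person. If one of ten saliva values is missing, the other nine are unused for that outcome. Amylase and cortisol are the H1 outcomes and STAI-S is the H3 outcome, so two of the four hypotheses rest on 10-cell analyses.

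The plan has little slack: it calculates a need for 38 and aims for 40. Each outcome could also be analysed on a different subset of people. With no rule written down, deletion, replacement or imputation could be chosen after the data are seen. The Protocol had already named a method, GEE, that accepts incomplete rows.

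**Working it through.** **Inputs from the documents.** f = 0.47, alpha 0.05, power 0.80, total 38, target 40 as 20 + 20 (Protocol 5.2). Five times and two sessions (SAP). Five samples at baseline (Protocol 6.0, Saliva Sampling: "we will collect a total of 5 saliva samples during this Baseline session"). For the follow-up: "The procedures for this session will precisely match the thresholding and baselining session but without the thresholding phase". The saliva text names six occasions but totals five; the example schedule and the SAP both support five.

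**Assumed input.** The chance p that a single value is missing, taken as 0.5% to 5% and independent across values. The documents give no rate.

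**1. The plan's own figure.** Two-group F test with 1 and N - 2 degrees of freedom and noncentrality f²N. At N = 38, noncentrality is 0.2209 x 38 = 8.39 and power is 0.805; N = 36 gives 0.782. So 38 is reproduced, as a two-group test of a single measure. N = 40 gives 0.826, 39 gives 0.815 and 37 gives 0.794. Power falls below 0.80 when a third person is lost.

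**2. Cells per outcome.** Amylase, cortisol, STAI-S: 2 x 5 = 10. Heart rate, heart rate variability, respiration, pupil diameter: 2 x 2 = 4. Cognitive outcomes: 2.

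**3. Complete participants, 10-cell outcomes.** Share complete = (1 - p)^10; expected number = 40 x share.

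| p | share complete | expected of 40 | whole N used | power at f = 0.47 |
|---|---|---|---|---|
| 0.5% | 0.951 | 38.0 | 38 | 0.805 |
| 1% | 0.904 | 36.2 | 36 | 0.782 |
| 2% | 0.817 | 32.7 | 33 | 0.744 |
| 3% | 0.737 | 29.5 | 29 | 0.684 |
| 5% | 0.599 | 23.9 | 24 | 0.595 |

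With fewer cells the loss is smaller. At p = 5%, four cells give 40 x 0.95^4 = 32.6 and two cells give 40 x 0.95^2 = 36.1.

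**4. If missing values cluster within people.** Under a beta-binomial model with an assumed within-person correlation of 0.2 or 0.4, about 30 or 33 of 40 are complete at 5% overall loss (not 24), and about 36 or 37 at 2% (not 33).

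**5. If incomplete people are replaced.** Completers needed for 40 full rows = 40 / (1 - p)^10: 44.2, 49.0 and 66.8, so 45, 49 and 67 at 1%, 2% and 5%.

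**6. The mechanism.** In a simulated set of 40 people by 10 cells, with one value missing in each of two people, a wide-format repeated-measures ANOVA used 38 people (error df 36). A linear mixed model used all 40 people and 398 values. This was run with the R packages car and nlme; rstatix was not available.

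**7. What a mixed model keeps.** By generalised least squares, over several assumed within-person correlations, it retains about 99 to 100% of full-data information on Group x Session at 1% loss, 98 to 99.8% at 2%, and 95 to 99.5% at 5%.

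**8. Why the covariance matters.** Simulated with 20 + 20 people, 10 cells and no true effect, with assumed variances of 0.5 between people and 0.3 residual. With added participant-by-session variance of 0.1, 0.2 or 0.3, a model with a participant random intercept alone rejects Group x Session about 19%, 27% and 32% of the time at a nominal 5%. The ANOVA-type test stays near 5%.

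**The case against.** **The target is already stated as complete data sets, with up to 100 people enrolled.** If complete covers every saliva value, recruitment continues until 40 full rows exist and no power is lost. The documents allow that reading but do not define the term. On it, the cost is extra recruitment (step 5) and unused data from people who finished 20 sessions.

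**Independent loss is unfavourable.** This stands: clustering shrinks the loss (step 4).

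**The power is borrowed.** This stands. The f of 0.47 comes from a study of subjective anxiety. The sample size calculation is for a single measure, so no power was planned for amylase, cortisol or a three-way interaction. STAI-S, the outcome it fits best, is completed electronically (Protocol 17.0), so inadequate swabs cannot affect it. Sensor dropout bears on the 4-cell outcomes, and averaging over a minute or the whole task absorbs part of it.

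**ANOVA is permitted by the Protocol, and deletion is inferred.** Both are true. The SAP does not state that incomplete rows are dropped; this follows from the method. Its mean imputation covers removed outliers only. Extending it to lost samples would keep people in but understate variance.

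**A mixed model can do harm.** This stands for a participant random intercept alone (step 8). Baseline and follow-up are weeks apart, so participant-by-session variation is likely. The model must allow for it, because the SAP's sphericity correction goes when the ANOVA is replaced.

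**Conclusion.** The concern holds outcome by outcome. For amylase, cortisol and STAI-S, one missing value among ten removes that person from that outcome's ANOVA, and a method that avoids this is available at little cost.

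The size is conditional. Under independent loss, expected power falls below 0.80 once more than about 0.5% of values are lost, and is about 0.60 at 5%. This rests on an assumed loss rate, on f = 0.47 carrying over from anxiety, and on incomplete people not being replaced.

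A reader might infer three stronger things that the documents do not support:
- That a lost sample removes someone from the trial. No withdrawal criterion says so.
- That a mixed model would offset the expected 40-50% attrition. It cannot, since withdrawn participants' data are destroyed.
- That the analysed subset is biased. That is possible if loss depends on the response, but the calculation here assumes random loss and does not show it.

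**What to change.** For the repeated-measures outcomes, replace the mixed ANOVAs in the SAP with a linear mixed model:
- fixed effects Group x Session x Time, with Time levels as already defined for each outcome;
- restricted maximum likelihood with Kenward-Roger degrees of freedom;
- random participant and participant-by-session effects, or a less restrictive within-person covariance, and not a participant random intercept alone.

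The Protocol's GEE with a small-sample correction is an alternative. Leave missing values missing. Include every participant not withdrawn who has at least one value for that outcome. State what makes a data set complete for the recruitment target.

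The cost is SAP wording and a different R function. The covariance structure must be prespecified, and the analysis assumes that values are missing at random. Keeping withdrawn participants' data would need a separate protocol change and is not part of this fix.
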